## **1.0 OBJECTIVES**

#### **1.1 Primary Objectives:**

Phase I:

1. To determine the safety and MTD of bosutinib in combination with inotuzumab ozogamicin in patients with Ph+ ALL and CML in lymphoid blast phase that express CD22

Phase II:

1. To determine the efficacy of bosutinib in combination with inotuzumab ozogamicin in patients with Ph+ ALL and CML in lymphoid blast phase that express CD22

## **1.2** Secondary Objectives:

Phase I:

- 1. To determine the efficacy of bosutinib in combination with inotuzumab ozogamicin in patients with Ph+ ALL and CML in lymphoid blast phase that express CD22
- 2. To determine the duration of response of patients treated with this combination
- 3. To determine the overall survival of patients treated with this combination
- 4. To determine the effect of the level of pre-treatment expression of CD22 with response to this combination
- 5. To determine the efficacy of this combination according to pre-treatment mutation status in the abl kinase domain
- 6. To determine the minimal residual disease after treatment with this combination and its impact in long-term outcome

Phase II:

- 1. To determine the safety bosutinib in combination with inotuzumab ozogamicin in patients with Ph+ ALL and CML in lymphoid blast phase that express CD22
- 2. To determine the duration of response of patients treated with this combination
- 3. To determine the overall survival of patients treated with this combination
- 4. To determine the effect of the level of pre-treatment expression of CD22 with response to this combination
- 5. To determine the efficacy of this combination according to pre-treatment mutation status in the abl kinase domain
- 6. To determine the minimal residual disease after treatment with this combination and its impact in long-term outcome

# 2.0 BACKGROUND AND RATIONALE

The Philadelphia chromosome [t(9;22)(q34;q11)] (Ph+), is the most common cytogenetic abnormality in acute lymphoblastic leukemia (ALL) in adults. Up to 40-50% of ALL patients older than 60 years will be Ph+. Before the introduction of molecularly targeted therapy, Ph+ ALL was associated with lower remission rates and a very poor prognosis with a median survival of less than one year.

With the introduction of therapy using ABL-tyrosine kinase inhibitors (TKIs) targeted to the aberrant BCR-ABL protein, the outcome of Ph-positive ALL has improved substantially and has been the major treatment advance for adults with ALL in the past two decades. Imatinib, the first TKI developed for use in Ph+ leukemias, has been combined with combination chemotherapy by various groups and this has substantially improved both complete remission (CR) and disease-free survival (DFS) rates. The MD Anderson group was the first to report on the combination of imatinib with chemotherapy. The 3 year CR duration and OS rates were significantly improved with hyper-CVAD-imatinib therapy compared to historical controls treated with hyper-CVAD alone (68% vs. 24% and 54% vs. 15%, respectively, p < 0.001). Second generation TKI dasatinib has also been combined with hyper-CVAD chemotherapy with improved outcomes. In a report of 35 patients treated with hyper-CVAD + dasatinib, the CR rate of 94% was achieved with estimated 2-year OS of 64%. Similar results have been reported by other groups and early TKI therapy is now established as the standard treatment of Ph+ ALL. Ponatinib is a novel TKI with single-agent activity in patients with T315I mutations. Cortes and colleagues reported activity of ponatinib monotherapy in patients with Ph+ leukemias. The primary endpoint for the Ph+ ALL and CML in lymphoid blast phase disease phase was major hematologic response (MaHR), and was achieved in 31% of patients with CML in lymphoid blast crisis and 41% of patients with Ph+ ALL.

Bosutinib is a second generation TKI and is a dual Abl and Src kinase inhibitor. Bosutinib was recently approved for the treatment of adult patients with chronic, accelerated, or blast phase CML with resistance/ intolerance to prior therapy. In a phase I/II study in advanced Ph+ leukemia with resistance/ intolerance to imatinib, patients received single-agent bosutinib (500 mg daily). One hundred thirty four patients were enrolled (63 accelerated phase [AP], 48 blast phase [BP], 23 ALL). Non-hematologic treatment-related adverse events occurring in  $\geq$ 10% of pts were diarrhea (67%), vomiting (40%), nausea (37%), rash (20%), and fatigue (10%). Grade 3/4 adverse events of any causality occurring in  $\geq$ 5% of pts were diarrhea (6%), pneumonia (6%), elevated ALT (6%), vomiting (5%), and dyspnea (5%). Grade 3/4 hematologic toxicity of any causality were anemia (37%), neutropenia (46%), and thrombocytopenia (65%). For the evaluable patients with BP and ALL, major cytogenetic response and major molecular response occurred in 57% and 34% patients, respectively. Thus, bosutinib is an active agent for treatment of patients with advanced Ph+ leukemia.

CD22 expression occurs in >90% of patients with ALL. Inotuzumab ozogamicin (IO) is a CD22 monoclonal antibody bound to a toxin, calecheamicin, and has shown single-agent activity in

relapsed/refractory ALL. In a phase II study, patients were given IO at 1.8 mg/m2 intravenously every 3-4 weeks. Forty-nine patients were treated. The median number of courses administered were 2 (range 1-5) and the median time between courses was 3 weeks (range 3-6). The overall response rate was 57% (CR 18%, marrow CR 39%). There were 7 patients with Ph+ ALL of which 3 (43%) had a response. Twenty-four percent patients had grade 1–2 and 4% had grade 3 increases in bilirubin. Grade 1–2 elevations of serum aminotransferase were noted in 55% patients and grade 3 elevations in 2% patients. Based on higher in vitro efficacy with more frequent exposure, a weekly schedule (0.8 mg/m2 day 1, 0.5 mg/m2 days 8 and 15, every 3-4 weeks) has been developed. With the weekly schedule (n=34), overall response rate was 53% (similar to 57% noted with the every 3 weeks schedule). With the weekly schedule, reversible grade 1–2 and 3–4 liver enzyme elevations were observed in 21% and 6%, respectively on the weekly dose. Thus, weekly schedule has similar efficacy as every 3 week schedule with improved toxicity profile.

Despite these advances with the introduction of TKI therapy and of the monoclonal antibodies such as IO, relapses are still major challenges in patients with ALL and long-term survival remains poor. As both TKIs and IO have shown independent clinical activity in patients with Ph+ ALL (and CML lymphoid blast phase), we hypothesize that combination strategy ('chemo-free' approach) would lead to improved clinical outcomes. We propose a phase I/II clinical trial with combination therapy with bosutinib and IO. If successful, this would represent a major advance in the management of patients with Ph+ ALL.

The present study will include patients with either Ph+ ALL or CML in lymphoid blast phase (CML-LBC). Both these disorders are characterized by increased number of lymphoid blasts in the marrow and the presence of the Philadelphia chromosome. The disease biology, clinical outcomes and management of patients with CML-LBC and Ph+ ALL is identical [NCCN guidelines (version 4.2013)]. The presence of Philadelphia chromosome defines these disease subgroups which are many times impossible to differentiate from each other (e.g., de-novo blast phase versus Ph+ ALL) and therefore, it is not surprising that many pivotal clinical trials of TKI therapy have included both these groups of patients.

Frontline Ph+ ALL Cohort: Outcomes of older patients with ALL remain suboptimal with longterm disease free control of <20% at 5 years. One of the major reasons for inferior outcomes in older patients is the risk of infection with standard chemotherapy. In analysis reported by O'Brien and colleagues, the risk of death in CR due to infections was 34%. Similar data have been reported by the UK ALL study group.

Low-intensity regimens have been reported to be effective and safe in patients with ALL. Use of antibody-drug conjugate inotuzumab and lower-intensity chemotherapy has been shown to be very effective in patients with Ph negative ALL (Jabbour et al. ASH 2015). Given suboptimal results with standard chemotherapy in older patients with ALL, and poor tolerability of chemotherapy in

older patients, there is a need to develop better therapy with non-chemotherapy approaches for this group of patients. We plan to include older patients with Ph+ ALL or CML-LBC for frontline treatment.

## 3.0 STUDY POPULATION

To be eligible for this study, patients must meet all criteria outlined below in Section 3.1 and Section 3.2.

## 3.1 Inclusion Criteria

1. Relapsed or refractory B-cell ALL or CML in lymphoid blast phase. Philadelphia chromosome must be present at screening (as determined by cytogenetic analysis, FISH, or PCR [i.e., BCR-ABL positive]). Note: patients with CML who have received treatment with tyrosine kinase inhibitors for their CML, and have progressed to lymphoid blast phase are eligible for frontline treatment.

Frontline Ph+ ALL or CML-LBC Cohort: Patients with newly-diagnosed Ph+ ALL or CML-LBC, who have received no or minimal treatment (minimal treatment is defined as treatment with steroids/hydroxyurea of  $\leq 2$  week duration; vincristine  $\leq 2$  doses; tyrosine kinase inhibitor of  $\leq 4$  week duration;  $\leq 2$  doses of cytarabine) and are  $\geq 60$  years or older are eligible. Patients must have bone marrow blasts >5% at the time of screening.

2. Expression of CD-22 in  $\geq$ 20% blasts

3. Age 18 years or older (For Frontline Ph+ ALL or CML-LBC Cohort: Age 60 years or older)

- 4. Eastern Cooperative Oncology Group (ECOG) Performance Status score of  $\leq 2$
- 5. The following baseline laboratory data:
  - Serum bilirubin  $\leq 2.0 \text{ mg/dl}$
  - Serum creatinine  $\leq 2.0 \text{ mg/dl}$
  - Alanine aminotransferase (ALT) and aspartate aminotransferase (AST)  $\leq 3 \times 10^{-10}$  x upper limit of normal (ULN)

6. Females of childbearing potential must have a negative serum or urine beta human chorionic gonadotrophin ( $\beta$ -hCG) pregnancy test result within 14 days prior to the first dose of study drugs and must agree to use one of the following effective contraception methods during the study and for 30 days following the last dose of study drug. Effective methods of birth control include:

- birth control pills, shots, implants (placed under the skin by a health care provider) or patches (placed on the skin)
- Intrauterine devices (IUDs)

• condom or occlusive cap (diaphragm or cervical/vault caps) used with spermicide Females of non- childbearing potential are those who are postmenopausal greater than 1 year or who have had a bilateral tubal ligation or hysterectomy.

7. Males who have partners of childbearing potential must agree to use an effective contraceptive method during the study and for 30 days following the last dose of study drug

8. Patients or their legally authorized representative must provide written informed consent

#### 3.2 Exclusion Criteria

- 1 History of another primary invasive malignancy that has not been definitively treated or in remission for at least 2 years. Patients with non-melanoma skin cancers or with carcinomas in situ are eligible regardless of the time from diagnosis (including concomitant diagnoses).
- 2 Patients with active unstable angina, concomitant clinically significant active arrhythmias, myocardial infarction within 6 months, or congestive heart failure New York Heart Association Class III-IV. Patients with a cardiac ejection fraction (as measured by either MUGA or echocardiogram) <40% are excluded.
- 3 Known evidence of active cerebral/meningeal disease. Patients may have history of CNS leukemic involvement if definitively treated with prior therapy and no evidence of active disease (defined as ≥2 consecutive spinal fluid assessments with no evidence of disease) at the time of consent.
- 4 Previous treatment with any anti-CD22 directed therapy
- 5 Patients with previous allogeneic stem cell transplant (SCT) if they meet either of the following criteria:
  - <100 days from allogeneic SCT
  - Active acute or chronic graft-versus-host disease (GvHD), or
  - Receiving immunosuppressive therapy as treatment for GvHD within the last 7 days
- 6. Patients with uncontrolled active infections (viral, bacterial, or fungal) are not eligible
- 7. Active hepatitis B or C infection, or known seropositivity for HIV

- 8. Patients with liver cirrhosis or other serious active liver disease or with suspected alcohol abuse
- 9. History of autoimmune diseases (such as systemic lupus erythematosus (SLE), Wegener's, Wegener's granulomatosis, polyarteritis nodosa). Note: Prior autoimmune diseases are allowed as long as clinically stable.
- 10. Prior chemotherapy/radiotherapy/investigational therapy within 2 weeks before the start of study drugs with the following exceptions:
  a. To reduce the circulating lymphoblast count or palliation: steroids, hydroxyurea. No washout necessary for these agents.
  b. For ALL maintenance/CML treatment: mercaptopurine, methotrexate, vincristine, single-agent, single-dose of cytarabine and/or tyrosine kinase inhibitors. These agents should be discontinued at least 48 hours prior to start of study drugs. (Note: the interval)

should be discontinued at least 48 hours prior to start of study drugs. (Note: the interval of time from last dose of any approved TKI to start of protocol treatment is 48 hours regardless of the indication for treatment with the TKI.)

- 11. Patients who have not recovered from acute non hematologic toxicity (to  $\leq$  Grade 1) of all previous therapy prior to enrollment
- 12. Females who are pregnant or lactating
- 13. Other severe acute or chronic medical or psychiatric condition or laboratory abnormality that in the opinion of the investigator may increase the risk associated with study participation or investigational product administration or may interfere with the interpretation of study results and/or would make the patient inappropriate for enrollment into this study.
- 14. Patients previously exposed to bosutinib are eligible unless they carry T315I
- 15. Patients with T315I mutations will be excluded (This criteria is not applicable for the frontline Ph+ ALL or CML-LBC cohort)

## 3.3 Discontinuation of Study Drug

A patient's treatment with study drug may be discontinued for any of the following reasons:

- Clinically significant progressive disease
- Adverse events that are not manageable with dose adjustments and/or optimal medical management, or that, in the opinion of the investigator, pose an unacceptable risk for the patient.
- Investigator decision

- Patient decision (e.g., withdrawal of consent)
- Study termination by Sponsor

Patients who discontinue from the study for disease progression or initiation of new therapy are considered to have completed the study per protocol. Patients who discontinue study treatment will be contacted about every 12 weeks (for up to one year) and asked about any anti-cancer therapy they may be receiving.

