- **4.1.1.4 Transition to the every 4-weekly schedule** In order to decrease the toxicity of the subsequent cycles, once a response is confirmed (CR, CRi, or whenever CCyR and/or absence of MRD by flow cytometry is documented), subsequent cycles will be administered at a dose of 1.0 mg/m^2 once every 4 weeks. Note: Patients who have been switched to every 4 weeks schedule may return to the weekly schedule if there is concern about recurrence of the disease.
- **4.1.1.5** Patients who experience a clinical benefit (CR/CRi/PR) with acceptable toxicity can receive up to a total of 6 cycles of inotuzumab ozogamicin. Treatment with bosutinib should continue indefinitely as long as patient is tolerating it well and responding to it.
- **4.1.1.6** Bosutinib will be dose-escalated in subsequent cohorts in a standard 3+3 study design (see Section 11.2).

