- 8. Disease assessment by bone marrow samples (aspirate and/or biopsy) should be done at screening, end of cycle 1 (before start of cycle 2), and then before of start cycles 3-6. Note: Once CR/CRi is achieved, bone marrow will repeated every 2 cycles, or as clinically indicated. For patients who continue bosutinib as monotherapy (after completing all 6 cycles of inotuzumab or if inotuzumab is discounted early), bone marrow will be repeated every 3 months. ABL-kinase domain mutation analysis will be performed at baseline (except in patients on the Frontline Ph+ ALL or CML-LBC cohort) and may be repeated after starting treatment, as clinically indicated. Peripheral blood (or bone marrow) PCR for BCR-ABL would be obtained at baseline and prior to start of each cycle.
- 9. CD22 immunophenotyping performed at screening on peripheral blood or bone marrow aspirate. CD22 immunophenotyping will be performed in follow-up bone marrow to assess for minimal residual disease.
- 10. End of Treatment Visit should occur 28 days (±10 days) after last dose of study drugs. For patients who cannot come for the clinic visit, a phone call to assess for any sideeffects will be done. Final study visit assessments will be performed before any other therapeutic intervention, if possible.
- 11. These procedures will not be performed on patients who cannot come to MD Anderson for their final study visit.
- 12. The schedule of Inotuzumab could be days 1, 8, and 15 OR once every 4-weeks (please see Section 4.1 for details)

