# **11.1.2 Secondary Endpoints:**

Phase I:

1. Overall MaHR

2. Duration of response and overall survival

Phase II:

- 3. Incidence and severity of adverse events
- 4. Duration of response and overall survival

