## **11.3 Statistical Analysis Plan**

The primary end-point is major hematologic response. The response will be evaluated along with its 95% confidence interval. Data from all subjects who receive any study drug will be included in the safety analyses. Subjects who entered the study and did not take any of the study drugs and had this confirmed will not be evaluated for safety. The severity of the toxicities will be graded according to the NCI CTCAE v4.0 whenever possible. We will follow standard reporting guidelines for adverse events. Safety data will be summarized by category, severity and frequency.

Analysis of secondary endpoints will be predominantly descriptive statistics and will be interpreted as being exploratory and hypothesis generating. The duration of response and overall survival (OS) will be estimated using the method of Kaplan-Meier. Cox regression models will be used to determine the relationship with the time-to-events (e.g. OS) and the potential prognostic factors.

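### Overall survival beyond about one year after stopping treatment is at risk of informative censoring, most likely upward, because off-treatment contact ends at one year and does not list vital status

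*Combined protocol and SAP*

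**What the plan says.** Follow-up after treatment is set out in section 3.3. Patients who stop study treatment "will be contacted about every 12 weeks (for up to one year) and asked about any anti-cancer therapy they may be receiving". The sentence before it says: "Patients who discontinue from the study for disease progression or initiation of new therapy are considered to have completed the study per protocol".

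Follow-up on treatment has no fixed end for those doing well. Section 4.1.1.5, repeated for the frontline cohort in 4.1.1.7, says: "Treatment with bosutinib should continue indefinitely as long as patient is tolerating it well and responding to it". For patients on bosutinib alone, the footnotes to the study calendar (section 8.0) add that "bone marrow will be repeated every 3 months".

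No other section supplies later survival follow-up. In the calendar the last scheduled contact is the final visit: "End of Treatment Visit should occur 28 days (±10 days) after last dose of study drugs". Serious adverse event reporting under section 10.1.5 runs to 30 days after the last dose, and beyond that only for treatment-related events.

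Section 11.1.2 lists "Duration of response and overall survival" as secondary endpoints in both phases. Section 11.3 gives the method: "The duration of response and overall survival (OS) will be estimated using the method of Kaplan-Meier". Neither section gives a start date, a censoring rule or a data cut-off for OS.

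**The concern.** Kaplan-Meier assumes that patients who leave observation have the same future risk of death as those who remain. Censoring everyone at a common calendar cut-off usually satisfies this. Here, scheduled contact is tied to the date of stopping treatment. A patient who does not respond would be expected to stop early and to leave scheduled contact about a year later. A patient who responds and tolerates bosutinib is seen indefinitely. If OS is censored when contact ends, the late risk set consists mainly of patients with the better prognosis, and the curve is too high from then on. A larger sample would not remove that error.

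The contact also names only one question, about anti-cancer therapy. Vital status is not listed, so even deaths within the year depend on what the caller happens to learn. Relapse is not listed either. Duration of response is therefore left incomplete for responders who stop in remission. This is a separate gap in data collection.

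**Working it through.** The plan states no assumed survival, event count or follow-up time for OS, so there is no OS figure to reproduce. The check is how far the Kaplan-Meier limit departs from true survival if the contact schedule is followed as written and OS is censored when contact ends.

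**Inputs from the plan:** contact ends 12 months after stopping (3.3); responders continue bosutinib without a fixed end (4.1.1.5, 4.1.1.7); the target response rate is 50% (11.2).

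**Assumptions, not in the plan:** exponential survival in each group; non-responders stop at month 2, so contact ends at c = 2 + 12 = 14 months; responders are fully followed; deaths before month 14 are all learned; responder share p = 40-60%; median survival mR = 18-36 months in responders and mN = 4-8 months in non-responders.

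**Formulas.** With S_R(t) = 2^(−t/mR) and S_N(t) = 2^(−t/mN):

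- True survival: S(t) = p·S_R(t) + (1−p)·S_N(t).
- Kaplan-Meier limit up to c: equal to S(t), so no bias.
- Kaplan-Meier limit after c: S(c)·S_R(t)/S_R(c), because only responders remain at risk.

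**Base case** (p = 0.5, mR = 24, mN = 6):

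- S_R(14) = 2^(−14/24) = 0.6674 and S_N(14) = 2^(−14/6) = 0.1984, so S(14) = 0.5 × 0.6674 + 0.5 × 0.1984 = 0.4329.
- 24 months: true 0.5 × 0.5 + 0.5 × 0.0625 = 28.1%; Kaplan-Meier 0.4329 × 0.5/0.6674 = 32.4%. Excess 4.3 points.
- 36 months: true 0.5 × 0.3536 + 0.5 × 0.0156 = 18.5%; Kaplan-Meier 0.4329 × 0.3536/0.6674 = 22.9%. Excess about 4.5 points.
- 12 months: no difference, and the median (11.2 months) is unchanged.

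**Ends of the assumed range:**

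| p, mR, mN | 24 months: true / Kaplan-Meier | Excess | 36 months: true / Kaplan-Meier | Excess |
|---|---|---|---|---|
| 0.6, 18, 4 | 24.4% / 26.2% | +1.8 | 15.1% / 16.5% | +1.4 |
| 0.4, 36, 8 | 32.7% / 39.9% | +7.2 | 22.7% / 31.7% | +9.0 |

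**Other exit patterns** (large-sample simulation, 400,000 patients, 50% responders, medians assumed):

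- Responders stop at relapse and are followed for one year from then (median time to relapse 8-18 months; median survival 6-12 months, after relapse in responders and from the start in non-responders): the 24-month excess is +4.3 to +8.0 points.
- 80% of responders leave for transplant at month 4 (median survival 48 months with transplant, 18 months for other responders, 6 months for non-responders): the sign reverses, with Kaplan-Meier 34.2% against 35.5% true at 24 months, and 21.4% against 27.1% at 36 months.
- Same survival in both groups: no bias.

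**The case against.** The strongest reply is that the plan never says OS is censored at the last 12-weekly contact. That is inferred from the absence of any other follow-up, and deaths might be found in ways the document does not describe. This stands. It rules out saying that OS is biased upward as a fact, which a reader might infer from section 3.3. It does not remove the risk, because the only follow-up rule written down is the one that produces it.

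The direction is also not fixed. Bosutinib continues only while the patient tolerates it and responds, so the one-year window starts on stopping for any reason. The note at the end of section 4.1.1.7 anticipates transplant without giving numbers. Exits in remission pull the estimate down; exits at relapse push it further up.

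Three stronger readings are tempting, and the document does not support them:

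- *Patients who progress get no contact after the final visit, because they count as having completed the study.* Under that reading, 12-month OS in the base case would be 62.7% against 47.9% true. But the next sentence of section 3.3 applies the 12-weekly contact to patients who stop treatment, without excepting them. The wording should be made clear, but this figure is not the finding.
- *Duration of response and the objective on minimal residual disease and long-term outcome carry the same bias.* Duration of response is measured in responders only, so a contrast between responders and non-responders cannot bias it. The residual-disease objective is an association, not the pooled OS curve. The figures above apply to neither.
- *Relapse after transplant is wholly lost.* Section 3.3 does not name transplant as new therapy, and asking about anti-cancer therapy would reveal some relapses within the year.

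Finally, OS is secondary, and section 11.3 treats secondary analyses as descriptive and exploratory. With 28 patients per cohort, the Kaplan-Meier standard error at 24 months is about 9 points by simulation in the base case, so an excess of 4.3 points is under half a standard error. That limits the practical weight of the point. It does not justify leaving a systematic error in a reported curve when it is cheap to avoid.

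**Conclusion.** The concern holds as a risk, limited to late OS. With off-treatment contact ending at one year, vital status not listed and no OS censoring rule or cut-off, Kaplan-Meier OS beyond about one year after stopping (about month 14 if non-responders stop at month 2) is open to informative censoring. The likely direction is upward: about +2 to +7 points at 24 months, resting on the assumed responder share and medians above and on responders being fully followed. A reversal is possible if many responders leave in remission.

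OS before that time is unaffected, provided deaths are learned at the contacts. The MaHR and CR/CRi decision rules are also unaffected, because they rest on response during 4 cycles. The gap in relapse data for responders who stop in remission is real, but no size is computed for it.

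**What to change.** In section 3.3:

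- Add vital status with its date, relapse date and transplant date to each 12-weekly contact.
- Follow all treated patients for vital status until death or a common data cut-off, or make one vital-status check at that cut-off. State that this includes patients who progress or start new therapy. Except only those who withdraw consent to follow-up.

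In section 11.3:

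- Define OS: start date, death from any cause as the event, censoring at the date last known alive, and the data cut-off.
- If follow-up is not extended, report OS only to 12 months. Contact runs for a year after stopping, so every treated patient who stays in contact can be followed that long. Vital status still has to be recorded at the contacts.

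The cost is slightly longer calls or record checks for at most 80 patients at one centre, plus the protocol wording. Treatment does not change.
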